7.2.4 Adverse Events

Adverse events (AEs) are to be monitored throughout the course of the clinical trial. All AEs are to be reported on the Adverse Event Form of the eCRF with complete information as required. If AEs occur, the main concern will be the safety of the subjects. At the time of the ICF signature, each subject must be provided with the name and phone number of clinical trial center personnel for reporting AEs and medical emergencies.

7.2.4.1 Definitions

7.2.4.1.1 *Adverse events (AE)*

According to ICH E2A, an AE is any untoward medical occurrence in a subject or clinical investigation subject administered a pharmaceutical product and which does not necessarily have a causal relationship with this treatment. An AE can therefore be any unfavorable and unintended sign (including an abnormal laboratory value), symptom, or disease temporally associated with the use of a medicinal (investigational) product, whether or not related to the medicinal (investigational) product.

Thus any new sign, symptom or disease, or any clinically significant worsening of an existing sign, symptom or disease compared to the condition at the first visit (including disease treated), should be considered as an AE. Lack of efficacy is not considered as an AE.

Notes:

- Any new sign or symptom reported by the subject that appears after accidental or intentional overdose or misuse should also be reported as an AE.
- There should be an attempt to report a diagnosis rather than the signs, symptoms or abnormal laboratory values associated with the report of an AE. However, a diagnosis should be reported only if, in the Investigator's judgment, it is relatively certain. Otherwise, symptoms, signs, or laboratory values should be used to describe the AE.
- Pregnancy is not to be considered as an AE; however, is an important medical event that must be monitored as described in Section 7.2.4.2.4.
- Each new episode of a chronic disease (e.g. hay fever, allergy, etc.) from the screening visit should be reported as a new AE.

7.2.4.1.2 *Serious Adverse events (SAE)*

A SAE is any untoward medical occurrence that meets any of the following criteria :

- Results in death,
- Is life-threatening,
- Requires inpatient hospitalization or prolongation of existing hospitalization,

- Results in persistent or significant disability/incapacity, or
- Is a congenital anomaly/birth defect.

Important medical events that may not result in death, be life-threatening, or require hospitalization may be considered a SAE when, based upon appropriate medical judgment, they may jeopardize the safety of the subject, and may require medical or surgical intervention to prevent one of the outcomes listed in this definition. Examples of such events are intensive treatment in an emergency room or at home for allergic bronchospasm, blood dyscrasias, or convulsions that do not result in hospitalization.

Note:

The term “life-threatening” refers to an event in which the subject was at risk of death at the time of the event; it does not refer to an event that hypothetically might have caused death if it was more severe.

Inpatient hospitalization is considered to have occurred if the subject has had to stay for a night at the hospital. The criterion for prolongation of hospitalization is also defined as an extra night at the hospital. Hospitalization may not constitute sufficient grounds to be considered as an SAE if it is solely for the purpose of diagnostic tests (even if related to an AE), elective hospitalization for an intervention that was already planned before subject enrolment in the clinical trial, admission to a day-care facility, social admission (e.g., if the subject has no place to sleep), or administrative admission (e.g., for a yearly examination).

7.2.4.1.3 *Adverse Events of Special Interest (AESIs)*

An AESI is a noteworthy event for the particular study drug that can be appropriate to monitor closely. It could be serious or non-serious.

The AESIs for this clinical trial have been defined as follows:

- Elevated ALT or AST (> 3 ULN) in combination with elevated bilirubin > 2 ULN, whether or not considered as related to the study drug by the investigator
- Elevated CPK (≥ 2.5 ULN), if considered as related to the study drug by the investigator
- Asthma or worsening of asthma ; this AESI will have to be reported within 24 hours, see Section 7.2.4.2.3
- IRR (local and systemic reactions, including hypersensitivity)
- Peripheral edema
- Skin or systemic infection
- Headache
- Exacerbation of AD, in subjects with medical history of AD

Study treatment should be permanently discontinued if asthma/worsening of asthma is reported as a serious adverse event, and may be temporarily discontinued for non-serious cases based on the judgment of the investigator, until return to the baseline condition. Refer to Section 7.2.4.2.3 for the procedures to be followed in case of new occurrence or worsening of asthma.

If applicable, additional information may be required (e.g. photo documentation of the AE) to allow a better evaluation and understanding of the above listed AEs.

7.2.4.1.4 *Unexpected adverse drug reaction*

According to ICH E6, an unexpected adverse drug reaction is defined as an adverse reaction, the nature or severity of which is not consistent with the applicable study drug information (e.g. Investigator's Brochure for an unapproved investigational product or the package insert/summary of product characteristics for an approved product).

7.2.4.1.5 *Adverse event reporting period*

The clinical trial period during which AEs must be reported is starting from the subject's signature of the Informed Consent Form to the end of the subject's participation.

The Sponsor should be informed if the Investigator becomes aware of any unusual safety information or any safety information that appears to be drug-related involving a subject who has participated in a clinical trial, even after the subject has completed the clinical trial. The Investigator should be diligent in looking for possible latent safety effects that do not appear until a medication has been discontinued.

7.2.4.1.6 *Severity*

Severity is a clinical determination of the intensity of an AE and not of a disease.

The Investigator is to classify the intensity of AEs using the following definitions:

Mild	Awareness of signs or symptom, but easily tolerated.
Moderate	Discomfort, enough to cause interference with usual activity
Severe	Incapacitating with inability to work or perform usual activity

7.2.4.1.7 *Relationship to the study drug(s) and/or clinical trial procedure*

The Investigator is to determine whether there is a reasonable causal relationship between the occurrence of the AE and exposure to the study drug(s) (i.e. nemolizumab or placebo) and/or study procedure (e.g. injection, blood sample collection). Medical judgment should be used to determine the relationship, considering all relevant factors including the pattern of reaction,

temporal relationships, positive dechallenge or rechallenge, relevant medical history, and confounding factors such as co-medication or concurrent diseases.

The expression “reasonable causal relationship” is meant to convey in general that there are facts or arguments to suggest a causal relationship (ICH E2A, Section IIIA 1).

The relationship assessment for an AE is to be completed using the following definitions:

Reasonable possibility:

According to the reporting Investigator, there is a reasonable possibility (i.e., suggestive evidence or arguments) that there is a causal relationship irrespective of the dose administered:

- Between the study drug (nemolizumab or its placebo) and the AE, and/or
- Between a clinical trial protocol procedure (e.g. injection, blood sample collection) and the AE

No Reasonable Possibility:

No suggestive evidence or arguments can be identified regarding a causal relationship between the study drug or a clinical trial protocol procedure and the AE.

7.2.4.2 *Reporting procedures*

7.2.4.2.1 *Procedures for reporting Adverse Events*

The collection of AEs is from the time that a subject signs the ICF to their final visit.

At each post-enrolment visit, the Investigator (or sub-Investigator) will question the subject about AEs using an open non-persuasive question to elicit reporting of AEs, for example “Have you noticed any change in your health since the last visit?” Directed questioning and examination will then be performed as appropriate.

Any AE occurring during the AE reporting period, whether it is related to the study drug(s) and/or study procedure(s) or not, will be recorded immediately in the source document, and described on the Adverse Event Form of the eCRF along with the date of onset, severity, relationship to the study drug(s) and/or study procedure(s), and outcome, without omitting any requested and known information. Additional information will be requested under certain circumstances (e.g. for AESI).

Adverse Events (AEs) assessed as related to the treatment or study procedure will be monitored until they have resolved or reached a stable condition. Other AEs will be monitored until the last visit if they have not resolved or reached a stable condition.

Reporting procedures for SAEs (see Section 7.2.4.2.2), AESI to be reported within 24 hours (see Section 7.2.4.2.3), and pregnancies (see Section 7.2.4.2.4) must be followed.

7.2.4.2.2 *Procedure for reporting a Serious Adverse Event*

For a SAE occurring during the clinical trial, regardless of whether it is related to the study drug and/or study procedure or not, the Investigator must :

1. Take prompt and appropriate medical action, if necessary. The safety of the subject is the first priority.
2. Ensure that the event is classified as an SAE. **Immediately** complete the AE and SAE form in the eCRF. This will generate an automatic email alert to Galderma Pharmacovigilance and to the Global Medical Services (GMS) within the CRO. The demographics, medical history, drugs/therapies form, and medical and surgical procedures form must also be completed and available for review in the eCRF at that time. *(Of note, in case there is no access to the eCRF, please refer to the instructions in your Investigator Site File for reporting an SAE).*
3. If required, contact the GMS within the CRO to discuss further actions to be taken; see contact details below:

**Investigator contact:
Clinical Safety Officer**

CRO Safety mailbox: [contact]

4. Send any relevant information or anonymized medical records (e.g. laboratory test results) to the GMS within the CRO (see contact details above), within 24 hours of receipt of this relevant information.
5. Monitor and record the progress of the event until it resolves or reaches a stable condition, with or without sequelae. For all additional follow-up evaluations, complete an updated SAE form in the eCRF **within 24 hours** of receipt of the updated information.
6. Obtain and maintain in files all pertinent medical records, information, and medical judgments from colleagues who participate in the treatment and follow-up of the subject. If necessary, contact the subject's personal physician or hospital staff to obtain further details.
7. When the outcome of the event is known, complete an updated SAE form, if appropriate.
8. Prompt notification of SAEs by the investigator to GALDERMA is essential so that legal obligations and ethical responsibilities towards the safety of subjects are met. GALDERMA has a legal responsibility to notify both the local regulatory authority and other regulatory agencies about the safety of a product under clinical investigation. GALDERMA or its delegate (i.e. the CRO) will comply with country specific regulatory requirements relating to safety reporting to regulatory authorities, Institutional Review Board (IRB) / Independent Ethics Committee (IEC) and investigators. Investigator safety reports are prepared for Suspected Unexpected Serious Adverse Reactions (SUSARs)

according to local regulatory requirements and GALDERMA policy, and are forwarded to investigators as necessary. An investigator who receives an investigator safety report describing an SAE(s) or other specific safety information (e.g., summary or listing of SAEs) from GALDERMA or its delegate (i.e. the CRO) will file it with the IB and will notify the IRB/IEC, if appropriate according to local requirements.

Comply with the applicable regulatory requirement(s) related to the reporting of SAEs to the IRB/IEC.

7.2.4.2.3 *Procedure for reporting asthma/worsening of asthma*

In this study, AESIs have been defined as described in Section 7.2.4.1.3. Among these AESIs, new occurrence of asthma/worsening of asthma will have to be reported within 24 hours according to the procedure described below.

Whether new occurrence of asthma or worsening of asthma is assessed as related to the treatment or not, the Investigator is to do the following:

1. Take prompt and appropriate medical action, if necessary. The safety of subjects is the first priority.
2. Ensure that the event is evaluated as an AESI. **Immediately** complete the AE form in the eCRF. This will generate an automatic email alert to the GMS within the CRO. The demographics, medical history, drugs/therapies form, and medical and surgical procedures form must also be completed and available for review at that time. *(Of note, in case there is no access to the eCRF, please refer to the instructions in the Investigator Site File for reporting an AESI).*
3. Send any relevant information or medical records (e.g. laboratory test results) to the GMS within the CRO (see contact details in Section 7.2.4.2.2), **within 24 hours** of receipt of this relevant information.
4. Monitor and record the progress of the event until it resolves or reaches a stable condition, with or without sequelae. For all additional follow-up evaluations, update the AE form in the eCRF **within 24 hours** of receipt of the updated information.
5. Obtain and maintain in files all pertinent medical records, information, and medical judgments from colleagues who participate in the treatment and follow-up of the subject. If necessary, contact the subject's personal physician or hospital staff to obtain further details.
6. When the outcome of the event is known, update the AE form in the eCRF, if appropriate.

7.2.4.2.4 *Procedures for reporting pregnancies*

Any pregnancy occurring during clinical trials, where the fetus could have been exposed to the study drug, must be monitored until its outcome in order to ensure the complete collection of safety data.

If a subject becomes pregnant, the Investigator is to do the following:

7. **Withdraw the subject from the clinical trial. The subject must not receive any further injection of the study drug.**
8. Complete as fully as possible the Pregnancy Surveillance Form – Part I: History and Start of Pregnancy, available in the eCRF. Print and send it by e-mail along with the exit form **within 24 hours** of receipt of the information, to the GMS within the CRO (contact see Section 7.2.4.2.2). *(Of note, in case there is no access to the eCRF, please refer to the instructions in the Investigator Site File for reporting a pregnancy).*
9. Monitor and record the progress of the pregnancy until its outcome. Contact the subject's regular physician (general practitioner or gynecologist) or hospital staff to obtain further details and ask for regular follow-up information.
10. Provide tri-monthly updates until the final outcome of the pregnancy, by completing the Pregnancy Surveillance Form – Part II: Course and Outcome of Pregnancy. For all additional follow-up evaluations, print and send the form by e-mail to the GMS within the CRO **within 24 hours** of receipt of the information. If the subject can no longer be reached (lost to follow-up), documentation of the non-response/contact with two phone calls and a letter (certified with return receipt) is required.
11. At the outcome of the pregnancy, complete as fully as possible the Pregnancy Surveillance Form – Part II: Course and Outcome of Pregnancy. Print and send the form by e-mail to the GMS within the CRO **within 24 hours** of receipt of the information.
12. If the pregnancy leads to an abortion (voluntary abortion, spontaneous abortion or therapeutic abortion), *in utero* death or congenital anomaly, follow the procedure for declaration of an SAE (see Section 7.2.4.2.2).

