1.2 Drug profile

Nemolizumab is a humanized monoclonal modified immunoglobulin G (IgG) 2 antibody comprising a structure of two H-chains (445 amino acid residues) and two L-chains (214 amino acid residues) connected by 16 disulfide bonds.

Please refer to the Investigator's Brochure (IB) for detailed information on non-clinical and clinical studies. Two clinical studies have been completed and reported for nemolizumab (Phase 1: CIM001JP; and Phase 2a: CIM003JG). In addition, one Phase 2 clinical study in uremic pruritus has been recently completed, but its clinical study report is not yet available (Phase 2: CIM106JP). Final data from studies CIM001JP and CIM003JG and preliminary data from study CIM106JP are summarized below.

The safety, tolerability, and pharmacokinetics of a single subcutaneous dose of nemolizumab were evaluated in a randomized, double-blind, placebo-controlled phase 1 study including 80 healthy volunteers and 36 Japanese AD subjects (CIM001JP) (Nemoto et al. 2016). There were no deaths or serious adverse events (SAE) reported in the study, and no dose-dependent increase in the incidence of AEs was observed. In healthy volunteers, the incidence of AEs was comparable between the nemolizumab groups and the placebo group, with similar results for Caucasians and Japanese volunteers. Among the healthy Caucasian adult males, increased creatinine phosphokinase (CPK) was more common in the nemolizumab groups, but the CPK increase in most subjects could be explained by excessive exercise.

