The following adverse events have been defined as Adverse Events of Special Interest (AESI) for the study: elevated alanine aminotransferase (ALT) and/or aspartate aminotransferase (AST) combined with elevated bilirubin, elevated CPK, newly diagnosed asthma or worsening of asthma (to be reported within 24 hours), IRRs, peripheral edema, skin or systemic infection, headache, and exacerbation of AD (for patients with medical history of AD).

Additional information regarding these events will be collected, when applicable.

Medical interview of signs and symptoms of asthma will be conducted in all subjects at each study visit, and a peak expiratory flow [PEF] measurement will be performed at each study visit on all subjects with a history of asthma.

In conclusion, when taking into consideration the potential benefit of nemolizumab in patients with PN, and the risk-minimization approaches implemented in the study, the benefit risk ratio of nemolizumab is considered favorable in this study.

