For each out-of-range laboratory result, the Investigator or designee will enter directly in the eCRF the Investigator judgment on the presence or the absence of a clinical significance.

All clinically significant out-of-range laboratory values for blood and/or urine samples collected at screening will be recorded in the medical history (report a diagnosis rather than an individual laboratory parameter abnormality whenever possible).

All clinically significant out-of-range laboratory values for blood and/or urine samples collected after screening, are to be reported as an AE if this abnormality was not present at the screening visit or is assessed as having worsened since the screening visit (i.e., there is a significant change from screening).

If the Investigator observes a clinically relevant laboratory test value, the laboratory tests will be repeated as soon as possible and monitored until the values have returned to normal and/or an adequate explanation for the abnormality is found. This does not apply to screening laboratory test values, except for TB test and CPK, which will be assessed at Screening 1 visit, and for which one retest is allowed at the Screening 2 visit (see [Table 2](#)).

In instances when a laboratory abnormality is reported as an AE or AESI, whenever possible, the Investigator is to provide a diagnosis rather than reporting individual laboratory abnormalities.

The following out-of-range laboratory values should be reported as an AESI (see Section [7.2.4.2.1](#)):

- Elevated ALT or AST (>3 ULN) in combination with elevated bilirubin (>2 ULN), whether or not considered as related to the study drug by the investigator;
- Elevated CPK (≥ 2.5 ULN) if considered as related to the study drug by the investigator.

A summary of sample volumes and the number of blood samples is detailed in [Appendix 1](#).

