### 5.8.3 Deaths, Other Serious Adverse Events, and Other Significant Adverse Events

Other significant TEAEs are those TEAEs reported as leading to permanent or temporary discontinuation of study treatment, leading to discontinuation of study, AESIs.

The following summaries will be produced:

- Summary of TESAEs by MedDRA SOC and PT based on 1) all causalities; 2) study drug related, and 3) study procedure (including TCS) related
- Summary of TEAEs associated with permanent discontinuation of study treatment by MedDRA SOC and PT based on 1) all causalities; 2) study drug related, and 3) study procedure (including TCS) related
- Summary of AEs associated with discontinuation of study participation by MedDRA SOC and PT based on 1) all causalities; 2) study drug related, and 3) study procedure (including TCS) related
- Summary of AESIs based on 1) all causalities; 2) study drug related

In addition, separate listings will be provided for the following:

- Deaths and other SAEs
- Permanent discontinuations of study treatment due to AEs
- Discontinuations of study participation due to AEs
- Temporary discontinuations of study treatment due to AEs
- AESIs

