#### **5.8.4 Clinical Laboratory Evaluation**

All laboratory values will be reported in SI units.

Laboratory data (absolute values and change from baseline) will be summarized descriptively by visit and treatment group.

In addition, the number and percent of subjects below, within, and above the laboratory reference ranges and the number and percentage of subjects who met criteria of PCSV (see Appendix 5) will be summarized by treatment group. Shift tables will be generated using the reference ranges. The shift will also be illustrated by the spaghetti plots.

A by-subject listing of all laboratory data will be provided by treatment group, with abnormal values flagged. Laboratory reference ranges should also be listed.

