Bilirubin total	µmol/L	mg/dL	>2.0 ULN and Baseline ≤2.0 ULN
CPK	U/L		>3.0 ULN and Baseline ≤3.0 ULN
Fibrinogen	g/L	mg/dL	Not provided
GGT	U/L		>2.5 ULN and Baseline ≤2.5 ULN
Albumin	g/L	g/dL	≤30 g/L and Baseline >30g/L
Uric acid *Male16-59			>600 µmol/L and ≤600 µmol/L at Baseline for Male;
*Female>16	mmol/L	mg/dL	>500 µmol/L and ≤500 µmol/L at Baseline for Female
*Male >60			
Cholesterol total	mmol/L	mg/dL	>10.34 mmol/L and ≤10.34 mmol/L at Baseline
Triglycerides	mmol/L	mg/dL	>5.7 mmol/L and ≤5.7 mmol/L at Baseline

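### For CPK, the all-causalities AESI summary can contain only events judged drug-related, and no planned table counts subjects at 2.5 ULN or more irrespective of causality

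*Protocol*

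**What the plan says.** **AESI definition.** Protocol 7.2.4.1.3 lists "Elevated CPK (≥ 2.5 ULN), if considered as related to the study drug by the investigator". Protocol 7.2.3 gives the same threshold with the same condition, "if considered as related to the study drug by the investigator", and SAP 4.2.3.5 carries both over. The liver item in the same list applies "whether or not considered as related to the study drug by the investigator". No other item on the list states a condition of relatedness to the study drug.

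**Risk/benefit section.** Protocol 1.4 gives the AESIs as including "elevated CPK, newly diagnosed asthma or worsening of asthma (to be reported within 24 hours"), with neither a CPK threshold nor a relatedness condition.

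**AESI tables.** SAP 5.8.3 plans a "Summary of AESIs based on 1) all causalities; 2) study drug related".

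**Laboratory tables.** SAP 5.8.4 plans values and changes by visit and arm, counts below, within and above the reference range, shift tables on those ranges, spaghetti plots, a listing, and "the number and percentage of subjects who met criteria of PCSV". The potentially clinically significant value (PCSV) for CPK in SAP Appendix 5 is ">3.0 ULN and Baseline ≤3.0 ULN".

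**Adverse event tables.** SAP 5.8.2 tabulates treatment-emergent adverse events (TEAEs) by preferred term for all causalities. A laboratory value becomes an adverse event only if judged clinically significant and new or worse since screening (Protocol 7.2.3, SAP 4.2.3.4).

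**Isoenzymes.** Protocol 7.2.3 triggers an isoenzyme test above 2.5 ULN whatever the cause. The SAP plans no specific table of these tests.

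**The concern.** In a blinded randomised trial, the difference between arms is the main evidence on causality. If each case must first pass an individual opinion on causality, events with a plausible alternative explanation drop out of the count, including any that belong to an excess on drug.

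CPK is exposed to this because exercise is an obvious alternative explanation. Protocol 1.2 reports that among healthy Caucasian adult men in phase 1, "increased creatinine phosphokinase (CPK) was more common in the nemolizumab groups, but the CPK increase in most subjects could be explained by excessive exercise". Protocol 8.2 anticipates the same explanation here, since subjects are told to avoid intensive exercise before CPK sampling.

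What is at stake is narrow. A reader of the all-causalities AESI table will take its CPK row at face value, and no other planned table gives the causality-free count at the level the plan itself uses for the AESI.

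**Working it through.** The point concerns definitions and planned outputs, so there is no figure in the plan to reproduce.

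**Step 1: the two AESI summaries.** Let A be the subjects with a CPK AESI, and R the subset judged drug-related. By definition every member of A is judged related, so A = R and the CPK rows are equal whatever the data. SAP 5.8.2 counts a missing relationship as related. Any such event flagged as an AESI would therefore fall in both summaries, and the equality still holds.

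**Step 2: where a post-baseline CPK value is counted.**

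| CPK value | Judged related | Judged unrelated |
|---|---|---|
| 2.5 to 3.0 ULN inclusive | Both AESI summaries; not PCSV | Neither AESI nor PCSV |
| Above 3.0 ULN, baseline 3.0 ULN or less | Both AESI summaries and PCSV | PCSV only |

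All four cells also enter the values, changes, reference-range counts and shifts, and the listing. They enter the TEAE tables only if reported as an adverse event. The reference-range tables pool every value above the upper limit, and the TEAE tables have no ULN threshold. No planned table therefore gives subjects by arm at 2.5 ULN or more irrespective of causality.

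**Step 3: how much the filter could hide.** The documents give no rate at 2.5 ULN or more, so the rates here are assumed. The arm size of 35 is the plan's (Protocol 9.3.3). With true rate p and share judged related r:

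- expected CPK AESIs = 35 × p × r
- chance of none in the arm = (1 − p × r)^35

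| p | r | Expected | Chance of none |
|---|---|---|---|
| 5% | 1 (no filter) | 1.75 | 0.95^35 = 17% |
| 5% | 0.5 | 0.88 | 0.975^35 = 41% |
| 5% | 0.2 | 0.35 | 0.99^35 = 70% |
| 15% | 1 (no filter) | 5.25 | 0.3% |
| 15% | 0.5 | 2.62 | 6.5% |
| 15% | 0.2 | 1.05 | 34% |

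**Step 4: effect on a difference.** Suppose 4/35 on nemolizumab and 1/35 on placebo reach the level (also assumed). The difference is 3/35 = 8.6 percentage points. If the share judged related is 0.5 or 0.2 in both arms, the table shows on average 8.6 × 0.5 = 4.3 or 8.6 × 0.2 = 1.7 points. The 4:1 ratio of expected counts is unchanged.

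**The case against.** **The comparison of CPK survives.** Relatedness decides only whether a rise carries the AESI label. SAP 5.8.4 compares CPK by arm with no causality filter, and SAP 5.2 brings repeat and unscheduled values into the PCSV determination. This stands. A reader might infer that the trial cannot say whether nemolizumab raises CPK. The documents do not support that: the values are collected and listed, and a post hoc count at 2.5 ULN remains possible.

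**Many of these rises should reach the TEAE tables.** Protocol 7.2.3 treats a value as clinically significant if, for example, it requires further diagnostic investigation, and it orders an isoenzyme test above 2.5 ULN. On a natural reading such a value becomes an adverse event, tabulated whatever its cause. This largely stands, but the judgement remains the investigator's, and the preferred-term row will not show how many subjects reached 2.5 ULN.

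**The prior signal is limited.** The phase 1 excess was in healthy Caucasian men after a single dose. For the phase 2a atopic dermatitis study, Protocol 1.2 lists CPK increase among events in 5% or more of treated patients. It does not name it among those more frequent than on placebo. Protocol 1.4 lists CPK under neither important nor non-important potential risks. All of this stands.

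**No differential bias is shown.** Causality is judged blind. The assumed 4/35 against 1/35 would give a two-sided Fisher p of about 0.36 even unfiltered. Protocol 5.4 excludes confirmed CPK above 1.5 ULN at screening, and the exercise advice may lower the share put down to exercise. This stands.

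**Two thresholds need not conflict.** An AESI trigger and a laboratory flag can serve different purposes, and Protocol 1.4 may simply be shorthand. That is fair, but it neither corrects the mislabelled row nor supplies the missing count.

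**Conclusion.** The point holds as a reporting defect. By construction, the all-causalities AESI summary is a related-only count for CPK. Values from 2.5 to 3.0 ULN judged unrelated fall outside both the AESI and PCSV tables, and those above 3.0 ULN judged unrelated appear in PCSV but not as AESIs. These conclusions rest on the definitions alone.

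The size cannot be fixed from the documents. Under the assumed 5% rate, a 35-subject arm would show no CPK AESI with probability 17% unfiltered, and 41% to 70% if between half and one in five are judged related.

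The consequence is under-counting and a misleading label. The randomised comparison of CPK is not lost, and differential bias is not shown. The change is worth making because it costs almost nothing.

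**What to change.** 1. In SAP 5.8.4 and Appendix 5, add a by-arm count of subjects with any post-baseline CPK of 2.5 ULN or more. Take it from laboratory data (scheduled, repeat and unscheduled values) and place it next to the existing 3.0 ULN row.
2. In SAP 5.8.3, either tabulate CPK AESIs irrespective of causality, keeping relatedness as a recorded attribute so that the two summaries can differ, or label the CPK row as related only. The first option also needs the wording changed in Protocol 7.2.3 and 7.2.4.1.3 and SAP 4.2.3.5. The second needs only the SAP.
3. Reconcile Protocol 1.4, 7.2.3 and 7.2.4.1.3 with SAP 4.2.3.5, 5.8.3 and Appendix 5. Which threshold is clinically right is for the sponsor to state.

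**Cost.** One table row and a label, or, with the first option, possibly a few more AESI forms. CPK counts may look less favourable. SAP 5.11 allows planned analyses to be revised before database lock.
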